3.0 OBJECTIVES

3.1 PRIMARY OBJECTIVE

The primary objective of this study is to examine the safety of long-term repeat exposure to rapastinel (GLYX-13) in subjects who participated in GLYX13-C-202.

The primary endpoint of this study is to examine the number of subjects who experience an AE over the course of the study.

4.0 SUBJECT POPULATIONS

Subject disposition will be summarized using all enrolled subjects, whether or not the study drug was received.

4.1 SAFETY POPULATION

The Safety Population will consist of all subjects who received any injection of study drug. All safety analyses will be based on this population.

4.2 FULL ANALYSIS SET

The Full Analysis Set will consist of all subjects who received any injection of study drug and who have at least 1 postbaseline efficacy assessment. All efficacy analyses will be produced using this population and it will be considered the primary efficacy population.

5.0 SUBJECT DISPOSITION

The number of subjects included in the Safety Population and Full Analysis Set will be summarized overall and by study center.

The number and percentage of subjects completing and prematurely discontinuing during the study will be presented overall. Reasons for premature discontinuation as recorded on the termination page of the electronic case report form will be summarized (number and percentage) overall for the Safety Population.

5.1 PROTOCOL DEVIATIONS

The number and percentage of subjects with significant protocol deviations will be summarized overall for the Safety Population. Protocol deviations will be defined, including significance classification, in the Protocol Deviation Requirement Specification.

6.0 DEMOGRAPHICS AND OTHER BASELINE CHARACTERISTICS

Demographic parameters (age, sex, ethnicity, race, weight) and other baseline characteristics will be summarized overall for the Safety Population.

Medical and surgical history, and psychiatric history will be summarized overall for the Safety Population. *Prior medication* will be defined as any medication started before the date of first dose of study drug. *Concomitant medication* will be defined as any medication taken on or after the date of first dose of study drug.

The use of prior medication will be summarized by the number and percentage of subjects receiving each medication within each therapeutic class and overall for the Safety Population. Concomitant medications will be summarized by the number and percentage of subjects receiving each medication within each therapeutic class and overall for the Safety Population. Multiple medication use of the same therapeutic class by a subjects will only be counted once. Prior and concomitant psychotropic medication, as well as any medications for the treatment of depression will be summarized for Safety Population.

The WHO Drug Dictionary Enhanced, will be used to classify prior and concomitant medications by therapeutic class and drug name.

7.0 EXTENT OF EXPOSURE AND TREATMENT COMPLIANCE

7.1 EXTENT OF EXPOSURE

Exposure to rapastinel for the Safety Population will be summarized descriptively overall for treatment duration, calculated as the number of days from the date of first study drug taken to the date of last dose taken, inclusively. Subject-years, calculated as the sum of the treatment durations of all subjects divided by 365.25, will also be presented overall similarly using descriptive statistics.

Quarterly dose and overall quarterly dose of study drug will also be summarized overall using descriptive statistics. Quarterly dose for a subject is defined as the total doses taken during 1 quarter interval. Overall quarterly dose for a subject is defined as the total doses divided by total number of quarters over the treatment period.

[figure not shown]

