7.2 MEASUREMENT OF TREATMENT COMPLIANCE

Dosing compliance for a specified period is defined as the total number of doses actually taken by a subject during that period divided by the number of doses that were expected to be taken during the same period multiplied by 100. The total number of doses actually taken during a specific time period is calculated as the sum of doses taken during that study period as obtained from the study medication exposure record. The number of doses expected to be taken for a specific study period will be the number of visits that a subject was prescribed rapastinel IV in that study period. Descriptive statistics for treatment compliance during each quarter and during the study period till the end of participation will be presented overall for the Safety Population.

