7.3 WEIGHT ADJUSTED DOSE OF RAPASTINEL

Per initial protocol, each subject received 5 mg/kg or 10 mg/kg in study GLYX13-C-203. In Amendment 3 of protocol, subjects originally assigned to 5 mg/kg in GLYX13-C-202 will receive 225 mg unit dose and subjects originally assigned to 10mg/kg in GLYX13-C-202 will receive 450 mg unit dose.

The dose of rapastinel for each subject will be divided by corresponding subject's weight assessed at the first visit at which each subject received either 225 mg unit dose or 450 mg unit dose and summarized descriptively by 225 mg or 450 mg treatment group for Safety Population. If subject had missing weight at that visit, the last non-missing weight assessment prior to that visit will be used in analysis.

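### Does SAP 7.1 need a unit for quarterly dose, since total doses could mean a number of injections or milligrams?

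*SAP*

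**What the plan says.** SAP 7.1 (Extent of Exposure) gives two definitions. The first is "Quarterly dose for a subject is defined as the total doses taken during 1 quarter interval". The second is "Overall quarterly dose for a subject is defined as the total doses divided by total number of quarters over the treatment period". On presentation it says "Quarterly dose and overall quarterly dose of study drug will also be summarized overall using descriptive statistics", so all dose levels and intervals are pooled. It states neither a unit nor the length of a quarter.

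The next two sections use related words. SAP 7.2 (Measurement of Treatment Compliance) works with the "total number of doses actually taken by a subject during that period" and adds: "The total number of doses actually taken during a specific time period is calculated as the sum of doses taken during that study period". It plans compliance summaries for each quarter as well as for the whole study. SAP 7.3 (Weight Adjusted Dose of Rapastinel) uses the singular: "The dose of rapastinel for each subject will be divided by corresponding" body weight, taken at the first visit with a fixed dose. The same section records the dosing history: "Per initial protocol, each subject received 5 mg/kg or 10 mg/kg in study GLYX13-C-203", replaced under Amendment 3 by 225 mg or 450 mg. Protocol 8.4 fixes the interval, weekly or biweekly, for the first month only. After that the investigator's treatment plan governs.

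**The concern.** The primary objective concerns the safety of long-term repeated exposure, so the exposure table is the background against which adverse events are read. The other exposure summaries in the available text say little about the amount of drug. Treatment duration and subject-years ignore dose size and interval, compliance is a ratio, and SAP 7.3 looks at a single visit. Quarterly dose is the one summary there that could show quantity over time, and its name suggests an amount.

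If it is a count, it cannot distinguish 225 mg from 450 mg, or show the move from weight-based to fixed doses. If it is milligrams, SAP 7.1 has no rule for turning a mg/kg dose into mg. Two programmers working from the same sentence could therefore produce tables that are not rescalings of each other.

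**Working it through.** The documents state no value for quarterly dose, so there is nothing to reproduce. The check has two parts: how far apart the two readings are, and which one the text supports.

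**Inputs.** Fixed doses of 225 and 450 mg (SAP 2.0, SAP 7.3). Scheduled end-of-quarter visits on Days 91, 182, 273 and 364, so 91 days apart (SAP Table 14.2-2). Assumptions: biweekly means every 14 days, dosing starts on Day 1, the interval holds all year, and no dose is missed.

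**Doses per 91-day quarter.** Weekly: 91 / 7 = 13. Every 14 days from Day 1: 7, 6, 7, 6 over four quarters, mean 26 / 4 = 6.5.

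**Milligrams = doses × mg per dose, mean per quarter.**

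| Regimen | Count | mg |
|---|---|---|
| 225 mg weekly | 13 | 13 × 225 = 2,925 |
| 450 mg weekly | 13 | 13 × 450 = 5,850 |
| 225 mg every 14 days | 6.5 | 6.5 × 225 = 1,462.5 |
| 450 mg every 14 days | 6.5 | 6.5 × 450 = 2,925 |

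The count hides a two-fold difference in mg between the weekly regimens. The mg total hides a two-fold difference in injections between 225 mg weekly and 450 mg every 14 days. For that last pair, the order reverses in a seven-dose quarter (13 against 7 doses; 2,925 against 7 × 450 = 3,150 mg). It agrees in a six-dose quarter (13 against 6 doses; 2,925 against 6 × 450 = 2,700 mg).

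**Which reading the text supports.** SAP 7.2 obtains a number of doses by summing doses taken over a period. SAP 7.1 uses almost the same plural expression, a total of doses taken over a quarter. SAP 7.3, the support for milligrams, uses the singular for the amount given at one administration. Compliance by quarter already needs the number of doses taken in each quarter as its numerator, which is quarterly dose read as a count. A count also needs no mg/kg conversion rule, so the lack of one fits a count.

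**The quarter.** SAP 7.1 does not define it. The 91-day spacing of scheduled visits is the natural choice. Table 14.2-2 also has a Quarter 1 window of Days 2 to 136. Weekly doses in it fall on Days 8, 15, …, 134, which is (134 − 8) / 7 + 1 = 19, or 20 with Day 1. That window assigns visit assessments to a nominal quarter. SAP 7.1 does not say to use it for dosing.

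**What depends on the choice.** The primary endpoint counts subjects with an adverse event (SAP 3.1). The tables in SAP 9.1 give numbers and percentages of subjects. Neither uses quarterly dose. The protocol synopsis rules out inferential analysis.

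**The case for a change.** The best case for a change is that the remedy is cheap and the gap is real. A few words would fix the unit. Reporting both the count and the milligrams would use dosing records and weights already planned, and would show what a count cannot: reductions from 450 to 225 mg, and the switch from mg/kg. The two dosing schemes coincide only at 225 / 5 = 450 / 10 = 45 kg. At body weight w, the mg per dose changes by 45 / w − 1 at the switch, for example −25% at 60 kg (an assumed weight), while the count does not move. The dose groups in SAP 2.0 place 5 mg/kg with 225 mg and 10 mg/kg with 450 mg, so they would not show the switch either.

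Part of this stands. No unit is printed, the label is loose, and on the count reading no table in the available text shows cumulative milligrams. But the percentages at the switch describe the change in dosing under Amendment 3 at assumed weights, not an error caused by the wording, and the number of subjects who switched is not given. Different ordering of subjects has no consequence where nothing orders them. A milligram row would be an addition to the plan, optional if a count was meant. It has its own weakness: it cannot tell a few large doses from many small ones, and any error in a carried-forward weight passes into it in proportion. Stating the unit alone would not make the table unique either, because the quarter would still be open.

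**Conclusion.** This is missing detail that the analysts will supply, not a rule that gives a wrong result. The likelier meaning is the number of injections, from the parallel wording in SAP 7.2. A milligram total would also be a legitimate description. Either is sound once the table carries its unit and the quarter length used.

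The two readings can differ two-fold for particular pairs of regimens, but only within one pooled descriptive table. The effect on the primary adverse event count is nil, and no test or comparison depends on the choice. The two-fold figures assume every-14-day biweekly dosing, full attendance and an interval kept for a full year, although the interval is fixed only for the first month. Parts of the SAP are not available for review, so exposure summaries elsewhere cannot be ruled out. The conclusion does not need them.

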7.2 MEASUREMENT OF TREATMENT COMPLIANCE

Dosing compliance for a specified period is defined as the total number of doses actually taken by a subject during that period divided by the number of doses that were expected to be taken during the same period multiplied by 100. The total number of doses actually taken during a specific time period is calculated as the sum of doses taken during that study period as obtained from the study medication exposure record. The number of doses expected to be taken for a specific study period will be the number of visits that a subject was prescribed rapastinel IV in that study period. Descriptive statistics for treatment compliance during each quarter and during the study period till the end of participation will be presented overall for the Safety Population.

7.3 WEIGHT ADJUSTED DOSE OF RAPASTINEL

Per initial protocol, each subject received 5 mg/kg or 10 mg/kg in study GLYX13-C-203. In Amendment 3 of protocol, subjects originally assigned to 5 mg/kg in GLYX13-C-202 will receive 225 mg unit dose and subjects originally assigned to 10mg/kg in GLYX13-C-202 will receive 450 mg unit dose.

The dose of rapastinel for each subject will be divided by corresponding subject's weight assessed at the first visit at which each subject received either 225 mg unit dose or 450 mg unit dose and summarized descriptively by 225 mg or 450 mg treatment group for Safety Population. If subject had missing weight at that visit, the last non-missing weight assessment prior to that visit will be used in analysis.

9.0 SAFETY ANALYSES

The safety analysis will be performed using the Safety Population.

The safety parameters will include AEs, clinical laboratory, vital signs, and ECG parameters. For each safety parameter, the last non-missing safety assessment before the first dose of study drug in study GLYX13-C-203 will be used as the baseline for all analyses of that safety parameter.

9.1 ADVERSE EVENTS

AEs will be coded using the *Medical Dictionary for Regulatory Activities* (MedDRA).

An AE (classified by preferred term) will be considered a treatment emergent adverse event (TEAE) if it was not present before the first dose of study drug or was present before the date of the first dose of study drug and increased in severity during the study period till the end of participation. If more than 1 AE was reported before the first dose of study drug and coded to the same preferred term, then the AE with the greatest severity will be used as the benchmark for comparison with the AEs occurring during the study. An AE that occurs more than 30 days after the date of the last dose of study drug will not be considered as a TEAE. An AE that becomes serious on or after the first dose of study drug will also be considered as TEAE.

The number and percentage of subjects reporting TEAEs will be tabulated by SOC and preferred term and further categorized by severity and causal relationship to study drug. If more than 1 AE is coded to the same preferred term for the same subject, the subject will be counted only once for that preferred term using the greatest severity and strictest causality for the summarization by severity and causal relationship. The distribution of TEAEs by severity and relationship to study drug will be summarized. An AE that occurs more than 30 days after the date of the last dose of study drug will not be summarized.

The incidence of common (in \geq 2% of subjects) TEAEs during the study period till the end of participation will be summarized by preferred term and will be sorted by decreasing frequency.

An SAE that occurred between the date of the first dose of study drug and 30 days after the date of the last dose of study drug, inclusive, will be considered a treatment-emergent SAE (TESAE). The number and percentage of subjects who have TESAEs will be summarized by preferred term. In addition, the incidence of on-therapy SAEs that led to death will be summarized separately by preferred term.

The incidence of TEAEs leading to premature discontinuation of study drug during the study period till the end of participation will be summarized by preferred term, and will be sorted by decreasing frequency.

Listings will be presented for all subjects with SAEs, subjects with AEs leading to discontinuation, and subjects who die (if any). All subjects with SAEs, including SAEs reported during the screening period and subjects discontinuing because of AEs occurring before the start of study drug, will be included in these listings.

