11 EFFICACY ASSESSMENTS

12.7 Adverse Events

Subjects should be queried in a non-leading manner, without specific prompting (eg, "How are you feeling?"). The site study staff should assess emerging symptoms of dissociative reaction similar to those caused by other NMDA antagonists including memory impairment, disturbance in time, body or environmental perception, stilted speech, emotional withdrawal, impaired coordination, motor retardation, bizarre reasoning or illusory experiences in any sensory perception, or confused state; such symptoms may be captured as adverse events.

An "adverse event" is any untoward, undesired, unplanned clinical event in the form of signs, symptoms, disease, or laboratory or physiological observations occurring in a human being participating in a clinical study with an investigational product, regardless of causal relationship. A "pre-existing" condition is one that is present before study drug dosing and is reported as part of the subject's medical history. Pre-existing conditions should be reported as an AE only if the frequency, intensity, or character of the pre-existing condition worsens during the course of the study.

Laboratory abnormalities are not considered AEs unless they are associated with clinical signs or symptoms, or require medical intervention. However, a laboratory abnormality (eg, a clinically significant change detected on clinical chemistry, coagulation, hematology, urinalysis) that is independent from the underlying medical condition and that requires medical or surgical intervention, or leads to study drug interruption or discontinuation, must be considered an AE.

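### SAP 9.1 sets a pre-dose severity floor per preferred term without separating resolved from ongoing events, so non-serious recurrences can drop out of the TEAE tables

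*SAP*

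**What the plan says.** SAP 3.1 gives the primary endpoint as "the number of subjects who experience an AE over the course of the study". In the readable text, the incidence tables that serve it (SAP 9.1) count treatment-emergent events and treatment-emergent SAEs only.

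SAP 9.1 classifies AEs by preferred term. There are two main ways to qualify as a TEAE:

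- The event is new: it counts "if it was not present before the first dose of study drug".
- The event worsened: it "was present before the date of the first dose of study drug and increased in severity during the study period till the end of participation".

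A further sentence covers multiple earlier events. Its trigger is stated as "If more than 1 AE was reported before the first dose of study drug and coded to the same preferred term". When that trigger is met, the worst of those earlier events becomes the comparator: "the AE with the greatest severity will be used as the benchmark for comparison with the AEs occurring during the study".

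Serious events have their own routes. "An AE that becomes serious on or after the first dose of study drug will also be considered as TEAE", and treatment-emergent SAEs are defined by date alone, with no severity comparison. The listings that follow the tables cover SAEs, AEs leading to discontinuation and deaths, with no treatment-emergence condition.

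Under Protocol 12.7.1, AE collection starts when consent is signed. Under Protocol 12.7.2, a change in severity over several days is entered as a separate record with its own onset date.

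**The concern.** The test is whether a term was present or reported before first dose, not whether it was ongoing at first dose. No sentence makes a recurrence after resolution a new event. A mild headache that resolved during screening therefore puts that term under a severity floor, and a mild headache after an injection does not qualify. The floor lasts as long as the subject stays in the study.

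The benchmark is also the worst pre-dose record, not the state at first dose. Because severity changes get their own records, an event that was severe in screening, mild at first dose and moderate afterwards has worsened on drug but is not a TEAE.

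The study is open-label, descriptive and without a control arm, so absolute incidence is the result. The rule can only remove post-dose events, and no comparator offsets the loss.

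**Working it through.** **Inputs.** The documents state no figure for this point, so there is none to reproduce. From the documents: up to 100 subjects (SAP 12.0), a common-TEAE threshold of 2% of subjects (SAP 9.1), severity grades 1 to 4 (Protocol 12.7.2), and a last quarterly visit at Day 1820 with a window to Day 1865 (SAP Table 14.2–2). All event rates below are assumptions.

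**Step 1: the rule as written.** For a non-serious post-dose event in the same preferred term:

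| Pre-dose AE(s) in the term | Not counted | Counted |
|---|---|---|
| None | none | grades 1–4 |
| Grade 1 | grade 1 | grades 2–4 |
| Grade 2, or grades 1 and 2 | grades 1–2 | grades 3–4 |
| Grade 3 | grades 1–3 | grade 4 |

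If the event becomes serious, it counts in every row. With one pre-dose AE, the floor comes from the worsening condition. The benchmark sentence adds the worst-of-several rule.

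**Step 2: how long the floor lasts.** Nothing ends it. The planned windows run to 1820/365.25 = 4.98 years, or 1865/365.25 = 5.11 years at the outer edge.

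**Step 3: effect on one preferred term.** Let p be the share of subjects with the event after dosing and s the share of those masked by a pre-dose AE. The reported incidence is p(1 − s).

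- p = 20%, s = 5%: 0.20 × 0.95 = 19%.
- p = 30%, s = 10%: 0.30 × 0.90 = 27%.

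These amount to 1 and 3 subjects in 100. If s is read as everyone with a same-term pre-dose AE at equal or greater severity, the loss is an upper illustration, because some of them will later have a worse or serious event and be counted.

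Alternatively, let q be the share of subjects with a resolved pre-dose AE in the term and r the chance that it recurs non-seriously and never at higher severity. Expected masked subjects are 100 × q × r, and P(at least one) = 1 − (1 − qr)^100:

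| q | r | Expected masked | P(at least one) |
|---|---|---|---|
| 1% | 25% | 0.25 | 0.22 |
| 3% | 50% | 1.5 | 0.78 |
| 5% | 50% | 2.5 | 0.92 |
| 10% | 75% | 7.5 | >0.99 |

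**Step 4: the common-TEAE table.** At 100 subjects the threshold is 0.02 × 100 = 2 subjects. A term with 2 affected subjects drops out if 1 is masked, and a term with 3 drops out if 2 are masked.

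**Step 5: the any-TEAE count.** A masked subject is lost only without another TEAE. Suppose 10% of subjects have a masked event and a share o of them has another TEAE. The loss is 100 × 0.10 × (1 − o): 5 subjects at o = 50%, 2 at 80%, 1 at 90%.

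**The case against.** The strongest reply is that the gap is one of silence and that little escapes through it.

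- **Resolution is not mentioned.** A programmer could treat a recurrence as new, so exclusion is the literal reading and not an express instruction. This stands, and it is a reason to settle the wording.
- **Other routes remain.** A reader might infer that later events of equal severity are never counted. The documents do not support that: a rise in severity, seriousness or the SAE definition brings an event in. A non-serious AE of equal severity that leads to discontinuation is still listed, though it is missing from the TEAE discontinuation table.
- **Repeats do not add up.** A subject counts once per preferred term, so ten masked recurrences cost at most one subject for that term. Longer follow-up also gives more chance of a higher-grade event that restores the subject.
- **The source period may be short.** Benchmark events arise only between consent and first dose. SAP 2.0 requires procedures to be repeated if screening was more than 7 days before dosing, but the readable text gives no maximum or typical interval.
- **Some conventions lean the other way.** A missing post-dose severity is set to severe (SAP 14.6), and a start date lacking only its day in the first-dose month is set to the first dose (SAP 14.8). These affect incomplete records only.

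A reader might also infer that the SAP contradicts the protocol, which has pre-existing conditions reported as AEs "only if the frequency, intensity, or character of the pre-existing condition worsens during the course of the study". That does not follow. The protocol sentence governs when medical history becomes a reportable AE and does not define treatment emergence. Such a worsening may be the first AE under its term and so face no benchmark. Protocol 12.7.1 also does not list frequency or character among the attributes by which each AE is described.

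**Conclusion.** The concern holds in a limited form. Taken literally, SAP 9.1 leaves non-serious recurrences at or below the worst pre-dose severity out of every readable TEAE table, and those tables are what the plan offers for an endpoint defined on AEs generally. The direction is downward.

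The size is probably small: a few subjects per affected term, and fewer in an any-TEAE count, under the assumed rates. A reader might infer a material bias in the main safety result, but the documents give no rate of pre-dose AEs, recurrence or co-occurring TEAEs from which to show one. The practical effect is most visible near the 2% threshold, where one or two subjects decide whether a term appears. No test or decision rule is affected, because the study is descriptive.

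**What to change.** Amend the TEAE definition in SAP 9.1 to say:

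1. Any AE with a new onset from the first C-203 dose to 30 days after the last dose is a TEAE, including recurrence of a term whose pre-dose event had resolved.
2. The severity comparison applies only to AEs ongoing at first dose and uses their severity at that time.
3. A new record that only marks unchanged or reduced severity of an ongoing event is not a new onset. This is needed because Protocol 12.7.2 gives each severity change its own onset date.

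The seriousness clause and the SAE definition can stay as they are.

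The cost is a few sentences and a change to the TEAE flag, which must link successive records of the same event. TEAE percentages will be slightly higher, and some of the added events will be background recurrences unrelated to the drug.
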